APPENDIX A: PARTICIPANT ELIGIBILITY CHECKLIST	
APPENDIX B: STANFORD RADIATION DERMATITIS SCORING SYSTEM	
APPENDIX C: CTCAE Verson 4.03 For Radiation Dermatitis	
APPENDIX D: MODIFIED BRIEF PAIN INVENTORY	

PROTOCOL SYNOPSIS

TITLE	Randomized Study of Topical Dilute Hypochlorite for the		
	Prevention of Radiation Dermatitis in Head and Neck Cancer		
STUDY PHASE	Phase III		
STUDY REAGENT	1:1000 dilute hypochlorite solution (0.005%) administered to the skin prior to daily radiation therapy		
PRIMARY OBJECTIVE(S)	The primary objective is to determine whether prophylactic topical dilute HOCl reduces the proportion of patients who develop Grade E radiation dermatitis as scored on the Stanford Radiation Dermatitis Scoring System (SRDSS)		
SECONDARY OBJECTIVE(S)	 Secondary objectives are: To determine whether this agent delays the time to development of Grade E radiation dermatitis To determine whether this agent improves quality-of-life and pain scores associated with radiation dermatitis 		
TREATMENT SUMMARY	Eligible patients will be randomized to daily application of topical dilute hypochlorite versus placebo for 10 minutes within 3 hours prior to daily radiation treatment. When patients in either arm develop Grade E radiation dermatitis during the radiotherapy course, they will be switched to topical dilute hypochlorite treatment daily per standard of care. Patients will complete the Modified Brief Pain Inventory at study entry, at 40-50 Gy through the radiation treatment course, at the end of radiation treatment, and at the follow-up visit 3-12 weeks after radiation treatment.		
SAMPLE SIZE	170 Patients (85 patients per arm)		
STATISTICAL CONSIDERATIONS	Sample Size Calculation: From prior clinical experience, we anticipate that 80% of patients will experience Grade E radiation dermatitis with standard skin care. In order to detect a 20% reduction in patients with Grade E dermatitis (80% vs 60% in those treated with dilute hypochlorite solution) with a two-sided alpha of 0.05 and beta of 80%, 170 patients will be enrolled. Primary endpoint: The proportion of patients in each arm who develop Grade E radiation dermatitis (as defined by the Stanford Radiation Dermatitis Scoring System) during a course of		
	radiation therapy will be assessed using a multiple logistic regression model adjusting for type of chemotherapy (cisplatin, cetuximab, none). Secondary endpoints: Time to development of Grade E radiation dermatitis in each arm will be assessed using the Cox proportional hazards model adjusting for type of chemotherapy. QOL/Pain scores will be analyzed using a repeated measures model adjusting for type of chemotherapy.		

SCHEMA

LIST OF ABBREVIATIONS AND DEFINITION OF TERMS

AE	Adverse event
CRF	Case report/Record form
CTCAE	Common Terminology Criteria for Adverse
	Events
DSMB	Data Safety Monitoring Board
HOCI	Hypochlorite
IRB	Institutional Review Board
MBPI	Modified Brief Pain Inventory
RR	Response Rate
SAE	Serious adverse event
SRDSS	Stanford Radiation Dermatitis Scoring System

1. **OBJECTIVES**

1.1. Primary Objective

The primary objective is to determine the proportion of patients who develop Grade E radiation dermatitis (as defined by the Stanford Radiation Dermatitis Scoring System, See APPENDIX B) as an adverse effect of radiation therapy or chemoradiation therapy for a head and neck cancer when initiating the use of prophylactic HOCl at the start of therapy (experimental arm) compared to placebo (control arm).

1.2. Secondary Objectives

The secondary objectives include the time to development of Grade E radiation dermatitis and the quality-of-life and pain levels (as assessed by the Modified Brief Pain Inventory) in the control arm versus the experimental arm.

2. BACKGROUND

2.1 Study Disease

Radiotherapy is often used in combination with surgery and systemic therapy for the treatment of various malignancies. [1]. Although technological advances have allowed for more precision and accuracy in targeting malignant tissues, normal tissues unavoidably receive some radiation dose. For example, the skin overlying the target area receives incidental radiation, and up to 95% of patients can develop an acute reaction called radiation dermatitis [2, 3]. Radiation dermatitis develops when the skin is unable to repair itself in a timely manner upon repeated exposures to radiation [3-5]. Topical agents such as moisturizers, aloe vera, or corticosteroids can offer some relief of pain and irritation, however several randomized trials have demonstrated that they unfortunately do not prevent the onset of radiation dermatitis [1, 6-12]. For moderate-to-severe cases of radiation dermatitis, a break in the radiation treatment regimen is often required to allow time for the skin to heal. In addition to skin irritation and breakdown, patients can also experience significant pain and discomfort during this time. The only agent that has been shown in a randomized trial to significantly reduce the severity of skin reactions is a silicone dressing (Mepitel Film) [8]. While this was shown to reduce the incidence of moist desquamation in women undergoing radiotherapy treatments for breast cancer, it can cost up to \$85 for a package of 10 dressings, making this type of treatment unaffordable for many patients [13]. Thus, significant improvements in the treatment of radiation dermatitis, a common side effect of radiation treatment, are needed.

For patients with locally advanced head and neck cancer, chemoradiation has become standard of care [14-19]. Cisplatin is the standard agent for concurrent therapy; however, cetuximab, a molecular inhibitor of EGFR, is used as an alternative[20]. The addition of concurrent chemotherapy to radiation treatment has resulted in increased rates of Grade 3-4 radiation dermatitis ranging from 2-35% compared to 4-21% with radiation alone[14-20]. In addition, cetuximab is notorious for its significant skin toxicity and may potentiate radiation dermatitis as well with Grade 3-4 toxicity affecting 16-60% of patients undergoing concurrent treatment with radiation[21-23].

Radiation dermatitis is typically scored using the CTCAE Scoring System. A severity of Grade 2 indicates moist desquamation that is patchy or found in skin creases while Grade 3 indicates confluent moist desquamation away from skin creases. Moist desquamation in the head and neck region causes significant morbidity for patients: pain at the neck leading patients to alter their clothing at the neck line, inability to shower, lack of restful sleep, discomfort while eating, and feeling self-conscious when

being seen in public. There are multiple treatments for this complication, but practice varies by institution, and there is no established standard of care.

2.2 Study Agent and Rationale

A standard treatment for radiation-induced moist desquamation (regardless of Grade 2 or Grade 3 scoring by CTCAE) is dilute hypochlorite applied topically once or twice daily to the affected area. In this context, this treatment is given primarily for its antimicrobial properties.

Recently, Leung et al discovered another potential mechanism of action for dilute hypochlorite baths [9]. HOCl functions as an oxidant and can disrupt cellular signaling processes by oxidizing certain mediators [24]. Nuclear factor- κ B (NF- κ B) is a protein complex that plays a central role in many different processes, including inflammation, aging, skin development, and radiation response [24]. Radiation injury activates NF- κ B, which drives the cellular responses that can ultimately lead to radiation dermatitis [25, 26]. NF- κ B plays a role in normal skin homeostasis as well [12-17]. NF- κ B is also influenced by intracellular reduction-oxidation (redox) conditions [27]. NF- κ B's role in skin homeostasis and radiation injury suggests that it will be an attractive target for the treatment of radiation dermatitis. Because NF- κ B is a master regulator of inflammation, we hypothesize that dilute hypochlorite baths may function as an anti-inflammatory agent by modulating NF- κ B signaling and inflammatory responses in the skin [24].

Leung et al found that HOCl inhibits intracellular NF-kB signaling by oxidizing an upstream regulator without impairing global gene transcription and protein signaling. In the skin of mice, a single brief exposure to topical HOCl significantly blocked NF-kB signaling. An established mouse model of radiation dermatitis was then used to assess whether hypochlorite could ameliorate acute radiation dermatitis. Radiation dermatitis was reproducibly induced on the backs of 4-week-old C57BL/6 female mice with 6 Gy irradiation for 10 days. Mice were randomized to receive a 30-minute bath in water (control) or dilute HOCl prior to each exposure to ionizing irradiation. Skin was examined daily and assessed using Radiation Therapy Oncology Group (RTOG) criteria, which grades skin ulceration as the highest score (grade 4). Skin ulceration is defined as round excavations that result in the complete loss of epidermis and some portion of the dermis. Compared to the control group, HOCl treated animals had a significantly lower RTOG score with scores of 1.8 ± 0.24 and $4.0 \pm$ 0 with and without HOCl treatment, respectively, by day 30. While all control animals developed skin ulceration by day 20, none of the HOCl-treated animals developed skin ulceration even by day 30. Histological analysis of skin biopsies taken on day 14 revealed that the skin of irradiated control animals exhibited classical signs of radiation dermatitis, including a lichenoid infiltrate, loss of skin appendages, and epidermal/dermal swelling. In contrast, the skin of HOCl-treated animals was largely normal, with retention of skin appendages and a mild increase in dermal cellularity. Finally, irradiation of mice skin induced the expression of five well-established NF-kB-dependent genes, and HOCI exposure significantly diminished this response. From clinical, histological, and molecular perspectives, it appeared that dilute bleach baths attenuated acute radiation dermatitis in mice.

HOCl is a safe, well-characterized, inexpensive, and widely available topical agent. The rationale for the starting regimen of this study is based on the methods from the prior mouse work and prior published human studies. At dilute concentrations, hypochlorite is safe for human skin contact as demonstrated in a prior clinical trial using the same concentration [18]. Hypochlorite is stable under normal use and storage conditions [28]. It is a strong oxidizing agent and does react with household chemicals such as toilet bowl cleaners, rust removers, vinegar, acids, and ammonia containing products

to produce hazardous gases, such as chlorine and other chlorinated species [28]. Encounters with such products is not planned nor anticipated for this study.

2.3 Study Design

This is a single-institution, randomized, double-blind, placebo-controlled clinical trial to investigate the role of topical HOCl in preventing radiation dermatitis in patients undergoing radiation therapy for head and neck cancer.

Patients will be screened at the time of radiation oncology consultation. If eligible, patients will be offered participation and consented for enrollment. Per standard of care, simulation for radiation treatment and the treatment planning process will be performed over two weeks. Patients can be consented prior to or within 3 days following the start of radiation treatment. After consent, a baseline clinical skin assessment will be performed, and patients will be stratified by type of chemotherapy (cisplatin, cetuximab, or none) randomized to the control arm or the experimental arm. Randomization will be performed by the study coordinator and will not be disclosed to the patient or the treating physician. The experimental arm will apply daily topical dilute HOCl for 10 minutes within 3 hours prior to radiation treatment. The control arm will apply daily topical placebo (water) for 10 minutes within 3 hours prior to radiation treatment. Clinical skin assessments will be performed by the treating physician once weekly during the radiation treatment course per standard of care, and radiation dermatitis will be graded according to both the Stanford Radiation Dermatitis Scoring System and the CTCAE v4.03 Scoring System. On both study arms, when the patient develops Grade E radiation dermatitis per the Stanford Radiation Dermatitis Scoring System, defined as moist desquamation within the radiation treatment field, requiring treatment (not prophylaxis) with topical dilute HOCl, the patient will have met the endpoint of the study, and the patient will be switched to standard-of-care treatment for radiation dermatitis consisting of topical dilute HOCl applied daily. For patients who do not develop Grade E radiation dermatitis during the radiation treatment course, a final skin assessment will be performed +/- 10 days after the last day of radiation treatment. Photos of skin within the radiation treatment field will be taken at the time of each clinical assessment. In addition, enrolled patients will complete the Modified Brief Pain Inventory questionnaire at the time of randomization, at 40-50 Gy of radiation treatment, on the last day of the radiation treatment course +/- 10 days, and at the follow-up visit 3-12 weeks after the completion of the radiation treatment course.

There is currently no external sponsorship or funding for this protocol.

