3.2 Exclusion Criteria

3.2.1 Prior external beam radiation therapy (EBT) to the head and neck region or prior chemotherapy for head and neck cancer (induction chemotherapy and I-131 treatment NOT excluded)c

- 3.2.2 Patients whose physician-approved radiation treatment plan indicates a maximum prescription dose of less than 45 Gy
- 3.2.3 Patients with scleroderma or discoid lupus

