10.3.1 Measurement Methods

The primary outcome will be assessed and graded by the treating physician, a radiation oncologist, who will give an individual score of the irradiated area at baseline, once weekly during radiation treatment course, at the end of the radiation treatment course +/- 10 days, and at the patient's follow up visit 3-12 weeks after completion of the radiation treatment course. The final grading of radiation dermatitis for each time point will be subject to the inter-rater reliability processes described in Section 10.2.

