12.2 Sample Size Justification

The primary endpoint is the proportion of patients who develop Grade E radiation dermatitis (as defined by the Stanford Radiation Dermatitis Scoring System) in each arm during a course of radiation therapy. From prior clinical experience, we anticipate that 80% of patients will experience Grade E radiation dermatitis with standard skin care. In order to detect a 20% reduction in patients with Grade E radiation dermatitis (80% vs 60% in those treated with dilute hypochlorite solution) with Type I error of 0.05 and Type II error of 20% (power of 80%), 170 patients will be enrolled.

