12.3 Primary Analysis

The primary endpoint is the proportion of patients who develop Grade E radiation dermatitis (as defined by the Stanford Radiation Dermatitis Scoring System) in each arm during a course of radiation therapy. A multiple logistic regression model will be used controlling for type of chemotherapy (cisplatin, cetuximab, none).

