12.4 Secondary Analyses

Secondary endpoints include the time to development of Grade E radiation dermatitis and the qualityof-life and pain scores in each arm. Time to development of radiation dermatitis will be defined as time from Day 1 of radiation treatment to the first appearance of Grade E radiation dermatitis. This data will be summarized with Kaplan-Meier curves. A Cox proportional hazards model will be used to compare the treatment groups. The model will adjust for type of chemotherapy and other patient characteristics should they prove to be significant. A repeated measures model will be used to analyze the quality-oflife and pain scores. The model will adjust for type of chemotherapy and other patient characteristics should they prove to be significant.

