APPENDIX B: Stanford Radiation Dermatitis Scoring System

Grade	Clinical finding
Α	No skin change
В	Faint, barely detectable erythema
С	Follicular rash, hyperpigmentation, evolving erythema
D	Dry desquamation, brisk erythema
Ε	Moist desquamation
F	Bleeding, ulceration, and/or infection

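### The baseline SRDSS grade is recorded before randomisation but used neither for entry nor in the primary model, so patients with pre-existing in-field Grade E/F-type findings can be randomised and dilute the effect

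*Combined protocol and SAP*

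**What the plan says.** Sections 2.3 and 4.1 give the same order: consent, baseline skin assessment, stratification, randomisation. Section 2.3 reads "After consent, a baseline clinical skin assessment will be performed, and patients will be stratified by type of chemotherapy". Section 10.3.1 has the treating physician grade the skin, "who will give an individual score of the irradiated area at baseline", and 4.1 applies both the SRDSS and CTCAE at each skin assessment. A baseline value on the primary scale therefore exists before allocation.

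The eligibility text sets no limit on it. Section 3.1 admits adults with any head and neck cancer who are planned for radiation. The only skin-related exclusion in 3.2 is "Patients with scleroderma or discoid lupus", and the Appendix A checklist matches. Appendix B describes its grades by appearance: Grade E is moist desquamation and Grade F is "Bleeding, ulceration, and/or infection". Neither row requires a radiation cause.

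Section 12.1 stratifies by chemotherapy type only. The primary analysis in 12.3 reads "A multiple logistic regression model will be used controlling for type of chemotherapy (cisplatin, cetuximab, none", with no other covariate. Section 12.4 defines the time endpoint as "time from Day 1 of radiation treatment to the first appearance of Grade E radiation dermatitis". It lets the Cox model take in other patient characteristics if they prove significant, but does not name baseline grade.

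**The concern.** The trial asks whether a topical agent prevents a skin finding. A patient whose field already shows that finding, or the worse one, when allocated has little or nothing left to prevent. Such patients add to the denominator of both arms and carry almost no treatment information, so the observed difference shrinks.

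The plan collects what is needed to identify these patients before allocation and then leaves it unused. It also has no rule for handling such a patient once enrolled. What is at stake is power, and a treatment difference that understates the effect in patients who could benefit. The milder baseline grades (B to D) are the starting value of the primary scale, and leaving them out of the primary model may give up some precision.

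**Working it through.** **Inputs from the documents.** 85 patients per arm (Protocol Synopsis); Grade E in 80% of controls and 60% of the experimental arm (12.2); two-sided 0.05 (Protocol Synopsis); power 80%. The Synopsis has "with a two-sided alpha of 0.05 and beta of 80%, 170 patients will be enrolled" and 12.2 has "Type I error of 0.05 and Type II error of 20% (power of 80%), 170 patients will be enrolled". The Synopsis figure is evidently power, so 80% power is used here.

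**Input not in the documents.** q, the share of patients with in-field Grade E/F-type findings at baseline, taken as equal in the two arms because allocation is random. Values of 0% to 10% are assumptions.

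**Step 1: reproduce the plan's figure.** With the pooled two-proportion formula and mean rate 0.70:

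n per arm = [1.96 × √(2 × 0.70 × 0.30) + 0.8416 × √(0.80 × 0.20 + 0.60 × 0.40)]² / 0.20² = 81.2, so 82 per arm, 164 in total.

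The planned 170 is slightly more. At 85 per arm, power is 81.8% by the normal approximation and 82.2% by exact binomial enumeration of the pooled z test. The stated 80% is met with a small margin.

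**Step 2: dilute the rates.** Two extremes bracket how these patients might be scored.

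- Always counted as events: control q + (1 − q) × 0.80, experimental q + (1 − q) × 0.60.
- Never counted as events: control (1 − q) × 0.80, experimental (1 − q) × 0.60.

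In both, the 20-point difference becomes 20 × (1 − q) points.

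**Step 3: power at 85 per arm (exact binomial, pooled z test, two-sided 0.05).**

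| Assumed q | Patients of 170 | Rates if events | Power | Rates if never events | Power |
|---|---|---|---|---|---|
| 0% | 0 | 80 / 60 | 82.2% | 80 / 60 | 82.2% |
| 2% | 3.4 | 80.4 / 60.8 | 81.1% | 78.4 / 58.8 | 79.4% |
| 5% | 8.5 | 81 / 62 | 79.4% | 76 / 57 | 75.1% |
| 10% | 17 | 82 / 64 | 76.4% | 72 / 54 | 68.2% |

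The normal approximation agrees within about 0.7 points throughout. On that approximation, power falls below 80% above about 3% if these patients count as events, and between 1% and 2% if they never do.

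**Step 4: which remedy acts on the dilution.** Not enrolling these patients, and enrolling others in their place, returns power to the 0% row. Adding baseline grade to the model does not, because a patient already at the endpoint still contributes nothing about treatment. The covariate's role is precision among patients with Grades A to D.

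**The case against.** The strongest reply is that the endpoint wording already removes most of the harm. Section 1.1 counts Grade E as an adverse effect of radiation or chemoradiation. Section 2.3 requires it to develop in the field and to need treatment, and 12.2 and 12.3 place it during the radiation course. On a plain reading, a tumour ulcer or surgical wound present beforehand is not an event, and baseline scores and photographs are there for comparison. This stands. It means the always-an-event column needs a grader to attribute an old lesion to radiation. The never-an-event column is also a worst case, since a local ulcer does not stop moist desquamation from developing elsewhere in the field.

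Four stronger readings are tempting, and the documents do not support them.

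- *Patients will enter with radiation-caused Grade E.* This is nearly impossible: 3.2 excludes prior external beam radiation to the head and neck, and consent closes 3 days after treatment starts. The realistic route is a lesion of another cause. A zero or negative time in the Cox model would likewise need such a lesion to be scored as radiation dermatitis.
- *The comparison is biased in favour of the agent, or by the missing covariate.* Allocation is random, so pre-existing findings can only dilute. Omitting a baseline covariate costs precision and does not invalidate the comparison.
- *A patient scored F throughout is never scored E, so the endpoint fails here.* Whether Grade F without E counts applies equally to lesions that arise later. It is a separate endpoint-definition question.
- *No analysis could use the baseline grade.* The Cox model in 12.4 may adjust for further characteristics. That route depends on observed significance and does not reach the primary model.

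It is also fair to say that a large loss and a trivial cost cannot both be claimed: at 10%, about 17 patients would be turned away.

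**Conclusion.** The concern holds in a limited form. A grade on the primary scale is available before allocation, yet no entry criterion and no term in the primary model uses it, and nothing bars a patient whose field already shows Grade E/F-type findings from a non-radiation cause. The consequence is possible dilution towards no effect, with no added risk of a false positive. At an assumed 2% the loss is about 1 to 3 points of power (82.2% to 81.1% or 79.4%); at 5% it is about 3 to 7 points (79.4% or 75.1%). These figures rest on an assumed prevalence, on equal prevalence in both arms, and on two extreme scoring rules. The true loss could be negligible. The change is worth making because it is cheap and because a prevention trial should state that patients are free of the endpoint finding at entry.

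**What to change.** 1. Add to 3.2 and Appendix A that patients with SRDSS Grade E or F findings in the planned treatment field at the baseline assessment are not randomised. Appendix A is completed before registration, so state that this item is confirmed after the baseline assessment and before allocation.
2. Add the baseline SRDSS grade (A versus B or higher) to the logistic model in 12.3 and name it in the Cox model in 12.4, specified in advance and not dependent on significance. Say that the term is dropped if every patient falls in one category.
3. Optional: a sentence in 10.3 and 12.4 that only Grade E first reached after baseline counts. This mainly makes the existing wording explicit.

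The cost is a few lines of text, one covariate already collected, and a few otherwise eligible patients not enrolled. If a share q is turned away, the 142-week accrual estimate in 12.5 becomes 142 / (1 − q): about 145 weeks at 2%, 149 at 5% and 158 at 10%. The precision gain from the covariate is probably small, because baseline falls before radiation or within its first days and few patients may be above Grade A.
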